### a. Procedures

1500 participants (adults, undergraduate, graduate students) recruited by research personal at a booth set up on or near the Stanford University campus. They will have the option of completing the study at the booth, or scheduling an appointment to participate at LPCH at a later time to do all the study. If interested in the study, the research staff will gauge their preferred availability to participate in the study. During the day of their scheduled study appointment, the research assistant will review the study, go over the consent forms, and answer any questions they may have about the study. Exclusion criteria includes (i) patients who do not consent (ii) are currently taking beta blockers or other chronotropic heart medication(s) (iii) have a history of severe motion sickness (iv) currently have nausea (v) currently experiencing seizures (vi) are clinically unstable (vii) have taken pain medications in the last 12 hours Inclusion criteria includes (i) greater than 18 years of age (ii) English speaking (iii) hearing intact

#### PHASE 1

Part 1a: 3 groups of 250 healthy volunteers will be recruited for this 2 part study. Once they consent to participate in the study, the research personnel will do a Sensory perception threshold (time, amplitude) captured via biosensors (Neurometer). Then the first group of 250 participants will be randomized into either control arm (they will not receive any kind of distraction, no technologies) or the use of Virtual Reality. The second group of 250 will be randomized into Active VR, they will play a game or Passive VR, they will be watching a movie in the VR headset. And the third group of 250 will be randomized into Augmented Reality (AR) or VR. The three groups will wait 5 minutes and each participant will switch to the opposite group (i.e. in the first group, VR group will switch to no VR group). Part 1b: Ice bath: Participants immerse hand in ice bath and starting again with their original assigned group (see attached Dahlquist et al., 2007) and keep hand submerged as long as they can withstand the cold or until 4 minutes

have elapsed, whichever comes first. Participants will not be told of the specifics of the time limit, to avoid competitiveness and expectations and will be asked for pain scores every 30 seconds.

## PHASE 2

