Evaluating the Effectiveness of Immersive Technologies, Virtual Reality and Augmented Reality, to Increase Pain Threshold During Ice Immersion

NCT04196686
February 23, 2022

[name], Principal Investigator
Stanford University
Stanford, California 94305

Statistical Analysis Plan

Outcomes

The primary outcome was Virtual Reality (VR)'s effect on pain tolerance. The first secondary outcome was VR's effect on perceived pain intensity. Our final secondary outcome was to investigate the effects of VR on modulating sympathetic response in the presence of painful stimuli. We made no changes to trial outcomes after the trial commenced.

Measures

We assessed pain tolerance by measuring the duration that participants kept their hand immersed within the ice bath (in seconds). Given that the cold pressor test produces an uncomfortable experience, we considered longer duration within the ice bath to represent increased pain tolerance.

Our first secondary outcome, VR's effect on perceived pain intensity, was assessed by collecting pain scores from participants every 30 seconds while their hands were immersed. We measured pain scores on a 0-10 scale, where 0 represented no pain and 10 represented the most excruciating pain imaginable.¹

Our final secondary outcome, the effects of VR on modulating sympathetic response in the presence of painful stimuli, was assessed by analyzing SCRD (in microsiemens) per 30 second interval. We refer to each of these 30 second intervals as a separate epoch. Skin conductance is expected to increase with increasing sympathetic nervous system activity, as sympathetic activity increases sweat secretion to increase skin conductance.

Sample Size

We considered a hazard ratio of 0.6 to be clinically significant given that it would indicate an approximate 30% improvement in pain tolerance. Assuming an alpha of 0.05 and power of 80%, sample sizes of 30 people in the VR group and 59 people in the control group were needed to be adequately powered to an estimated hazard ratio of 0.6.

Randomization

We randomized participants to their first ice immersion intervention (VR or no VR) and hand use (dominant or non-dominant) using an electronic random number generator with a 1:1 allocation.² Participants then crossed over for their second ice immersion

Statistical Methods

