To analyze the effectiveness of VR on pain tolerance, we analyzed the survival time using a Cox mixed-effect model with trials nested in subject and fit using the coxme package using R software. We controlled for dominant hand treatment assignment, dominant hand order, and gender.

To analyze our secondary outcomes, we used linear mixed effects models with outcomes nested in subject using the lme4 package in R. We controlled for dominant hand treatment assignment, dominant hand order, and gender when analyzing pain perception. The variables in the physiologic model were SCRD change over time and the SCRD change between groups, defined as those with and without VR.

References

- [2] Suresh K. An overview of randomization techniques: An unbiased assessment of outcome in clinical research. *J Hum Reprod Sci*. 2011;4(1):8-11.

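### The SAP's 30 VR plus 59 control does not give 80% power at a hazard ratio of 0.6 (about 62% two-sided, 74% one-sided), and the crossover has no such groups

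*SAP*

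**What the plan says.** SAP, Sample Size: "We considered a hazard ratio of 0.6 to be clinically significant". The inputs follow, "Assuming an alpha of 0.05 and power of 80" per cent, and then the result: "sample sizes of 30 people in the VR group and 59 people in the control group were needed to be adequately powered". Sidedness, formula, expected number of events, within-person correlation and a reason for unequal groups are not given.

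SAP, Randomization: the first condition was assigned "using an electronic random number generator with a 1:1 allocation", and "Participants then crossed over for their second ice immersion". SAP, Statistical Methods: the primary analysis is a "Cox mixed-effect model with trials nested in subject".

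Protocol 2a, Procedures, Phase 1: a group of 250 is randomized between control and VR, and "each participant will switch to the opposite group". Immersion lasts "as long as they can withstand the cold or until 4 minutes" have passed. The sample-size paragraph at the end of 2a starts from means of 7 (SD 1.5) and 9, giving 10 per group and a target of 12 allowing for dropouts. After the first 24 participants the number was changed to 250 per group. No hazard ratio appears there.

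**The concern.** The sentence carries two separate problems. The group sizes look too small for the power claimed: with 30 in one group, 89 people carry less information than the same number split evenly. And in a crossover each participant supplies one immersion under each condition, so a 30-person VR group beside a separate 59-person control group cannot describe the planned comparison.

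The sentence is the SAP's only justification of size for its primary outcome. If it is wrong, the SAP does not tell a reader how many crossover participants were needed for a hazard ratio of 0.6 or what power that number gave. The only other size in the documents, the protocol's 250, comes from a different calculation.

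**Working it through.** **Inputs.** Hazard ratio 0.6, alpha 0.05, target power 80%, and 30 and 59 people all come from SAP Sample Size. Two inputs are missing. Sidedness is not stated, so both are shown. The number of events is not stated, so I assume that all 89 people withdraw before the 4-minute cap. This is the most favourable case, since any capped immersion lowers the event count.

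**1. Attempt to reproduce 80% (Schoenfeld).** Power = Φ(√(d·p(1−p))·|ln HR| − z), with d = 89 and p = 30/89 = 0.337.
- d·p(1−p) = 30 × 59/89 = 19.89, with square root 4.460; |ln 0.6| = 0.5108; product 2.278.
- Two-sided: 2.278 − 1.960 = 0.318, power **62.5%**.
- One-sided: 2.278 − 1.645 = 0.633, power **73.7%**.

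A log-rank simulation of 30 against 59 (exponential times, no censoring, 20,000 runs) gave 59.0% and 70.9%. The stated 80% is not reproduced.

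**2. Events needed for 80% at 30:59.** d = (z + 0.8416)²/(p(1−p)(ln 0.6)²), with p(1−p) = 0.2235 and (ln 0.6)² = 0.2609.
- Two-sided: 7.849/(0.2235 × 0.2609) = 134.6, so 135.
- One-sided: 6.183/(0.2235 × 0.2609) = 106.03, so 107.

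Both exceed 89, so a one-sided test does not rescue the sentence.

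**3. Layout.** Under 1:1 allocation of the first condition with everyone crossing over, n participants give n VR and n no-VR immersions from the same n people. The planned model pairs them within subject. Nothing in that design yields 30 people in one condition and 59 others in the other.

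**4. A possible source.** If 59 people each did both immersions, and the 118 immersions are counted as independent, uncensored events split evenly, then √(118 × 0.25) × 0.5108 = 2.774, and 2.774 − 1.960 = 0.814. Power is 79.2% two-sided. An exact 80% would need 7.849/(0.25 × 0.2609) = 120.3, so 121 events. The 30 could then be roughly half of 59, randomized to VR first. The SAP says none of this.

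**5. Against the protocol.** Three Phase 1 groups and three Phase 2 parts at 250 each make 6 × 250 = 1,500, the protocol's total. So 250 appears to be the number per comparison, including control against VR. On the same simplified basis as step 4, 250 people give 500 immersions: √125 × 0.5108 − 1.960 = 3.751, power above 99.9%. A harsher, sign-type comparison within pairs, still uncensored, takes the chance that the VR immersion is the longer as 1/(1 + 0.6) = 0.625. Then (0.125 × √250 − 1.96 × 0.5)/√(0.625 × 0.375) = 2.06, about 98%. The two documents therefore point to very different sizes and powers for one comparison.

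**The case against.** The strongest reply is that the sentence mislabels a sound calculation: 59 people crossing over come within a point of 80%. That is plausible, but it is conjecture. The sentence names people in two groups, and this reading treats paired immersions as independent and ignores the cap, while the planned model nests trials in subject. If it is the source, the sentence still needs correcting.

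A second reply is that another formula comes close. The nearest two-group variant tried is Freedman's formula, one-sided, with the 59 people on VR and the 30 on control: √(89 × 59/30) × 0.4/(1 + 0.6 × 59/30) − 1.645 = 0.783, power 78.3%. It reverses the sentence's own labels, so it does not support the sentence.

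A third reply is that the protocol does state a planned size. This stands: the documents as a whole are not silent on numbers. But 250 has a different basis and does not repair the SAP figure; it adds a conflict to be reconciled.

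A reader might infer from 62% that the trial was underpowered. The documents do not support that. The 62% belongs to a two-group trial that was not planned, the documents do not give the number enrolled, and at the protocol's 250 the simplified figures above are high. Power under the mixed model also depends on within-person correlation and on how many reach the cap, and neither is stated.

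**Conclusion.** The concern holds as an error in a stated power and size. Read literally, 30 and 59 give 62.5% two-sided or 73.7% one-sided at a hazard ratio of 0.6, against a stated 80%. This rests on proportional hazards and on every person having an event; any capping lowers both figures. The mismatch with a 1:1 crossover analysed within subject stands on the text alone, whatever formula is used, and so does the disagreement with the protocol's 250.

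The finding goes no further. It does not establish low power in the trial as run, and it does not touch the primary estimate or test. That the 59 were crossover participants remains a possibility, not a finding. The sentence should be corrected, as a reporting error with limited consequences.

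**What to change.** Remove 30 and 59 as a two-group figure. In its place, state the original calculation:
- what 30 and 59 count;
- the sidedness of alpha and the formula or software used;
- the number of participants each doing one VR and one no-VR immersion;
- the assumptions on withdrawal before the 4-minute cap and on within-person correlation.

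If the calculation cannot be recovered, say so. Correct the stated power to what those inputs deliver, and reconcile the size with the protocol's 250 by explaining which calculation governed the control-against-VR comparison. The SAP is written in the past tense, as though the immersions were done. Any new power figure for the crossover Cox mixed model should therefore be labelled as computed after the fact, with its assumptions declared, and not presented as planning.

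The cost is one recalculation and revised SAP wording, with no extra participants. The sponsor should accept that the corrected power may come out below 80%.

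### No model names a period term for the randomised crossover: a clear gap for SCRD, dependent on two undefined hand variables for the Cox and pain models; minor and free to fix

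*SAP*

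**What the plan says.** SAP, Randomization: "We randomized participants to their first ice immersion intervention (VR or no VR) and hand use (dominant or non-dominant"; allocation was 1:1. "Participants then crossed over for their second ice immersion". Each participant therefore has two immersions, one per condition, in random order.

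SAP, Statistical Methods: the primary analysis is a Cox mixed-effects model with a random effect for trials within participant. Its covariates are given as "We controlled for dominant hand treatment assignment, dominant hand order, and gender", and the same three are listed for the pain model. For the physiologic model, "The variables in the physiologic model were SCRD change over time and the SCRD change between groups", with groups defined by VR or no VR. Under Measures, time for that outcome is cut into 30-second intervals: "We refer to each of these 30 second intervals as a separate epoch".

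Period, sequence and immersion number appear in none of the three models, and the two hand variables are not defined. The protocol contains no analysis model. Its Procedures section, in the wording for Part 1a, says "The three groups will wait 5 minutes and each participant will switch to the opposite group".

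**The concern.** Tolerance, pain and skin conductance may differ between a first and a second ice immersion whatever the condition, and with only a few minutes between conditions this is plausible. In a two-period crossover a fixed effect for period removes that difference from the treatment comparison. Without it, the difference either goes into the residual variation or, when more participants happen to have VR second than first (or the reverse), moves the VR estimate. The SAP mentions no blocking and does not ask for the number of participants per sequence, so a reader could not judge how far the estimate may have moved.

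**Working it through.** The documents give no period effect, so there is no plan figure to reproduce. Every period effect below is an assumption.

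**1. Do the listed terms already contain period?** I took the fixed-effect columns over all combinations of treatment order and hand order, added a column for immersion 1 versus 2, and compared the matrix rank. If the rank rises, period is not covered. The hand is assumed to switch at the second immersion; the SAP does not say so.

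| Fixed effects | Rank without, with period | Period covered? |
|---|---|---|
| SCRD: intercept, VR | 2, 3 | No |
| SCRD plus sequence | 3, 4 | No |
| VR, gender, both hand variables per participant (dominant hand had VR; dominant hand went first) | 5, 6 | No |
| VR, gender, hand used at this immersion, dominant-hand-first | 5, 6 | No |
| Previous row plus hand used x dominant-hand-first | 6, 6 | Yes |
| Per-participant hand variables, all two-way interactions with VR and each other, gender | 8, 9 | No |
| Same with the three-way interaction | 9, 9 | Yes |

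If the hand-order variable simply means immersion number, period is in the model directly. In the SCRD model, epoch counts time within an immersion, and nothing says that epochs run on from the first immersion into the second. The random effect for participant is not a period effect either.

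**2. Effect on the Cox HR.** Inputs: true HR 0.60 (the SAP's target), so b = ln 0.6; g = ln(period HR), the hazard at immersion 2 relative to immersion 1; w = share of participants with VR second. In the paired limit (comparison within person, no censoring), the model without period estimates

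HR = exp(logit(w x expit(b+g) + (1-w) x expit(b-g))).

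For period HR 1.5: expit(b+g) = 0.9/1.9 = 0.4737 and expit(b-g) = 0.4/1.4 = 0.2857. With w = 0.6, 0.6 x 0.4737 + 0.4 x 0.2857 = 0.3985, and 0.3985/0.6015 = 0.6625.

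| Assumed period HR | 50/50 | 60/40 with VR mostly second | 60/40 with VR mostly first |
|---|---|---|---|
| 1.1 | 0.60 | 0.61 | 0.59 |
| 1.2 | 0.60 | 0.62 | 0.58 |
| 1.5 | 0.61 | 0.66 | 0.56 |
| 2.0 | 0.63 | 0.72 | 0.55 |

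For scale, suppose 89 crossover pairs. This is an assumption: it adds the SAP's two groups, "sample sizes of 30 people in the VR group and 59 people in the control group were needed", although in a crossover each person is in both. The paired standard error (SE) is 1/sqrt(89 x 0.375 x 0.625) = 0.22. The 60/40 shift at period HR 1.5 is ln(0.6625/0.60) = 0.10, under half of that.

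**3. How likely is such a split?** With simple 1:1 randomisation and no blocking, the chance of 60/40 or worse is 5.6% at n = 89 and 0.2% at n = 250 (the protocol's figure: "the first group of 250 participants will be randomized into either control arm"). The average departure from 50/50 is 4.2 and 2.5 percentage points.

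**4. False positives and power, Cox.** In the paired limit over random splits, the false-positive rate without period is 5.6% at n = 89 and 4.9–5.0% at n = 250 for period HRs from 1.0 to 2.0. The 5.6% is there with no period effect at all. A frailty-Cox simulation (n = 89, frailty SD 1.0, control mean 90 s, all assumed; the protocol's 240 s cap; 600 runs per setting) gave 4.0–4.5% without period and 4.2–5.5% with it. Power at HR 0.60 without and with period was 77.7% and 78.2% (period HR 1.2), 80.3% and 81.5% (1.5), and 75.5% and 79.0% (2.0). The Monte Carlo SE is about 1.7 points per estimate.

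**5. Linear models.** At 60/40 the estimate shifts by (0.6 - 0.4) = 0.2 times the period effect. Let r be the period effect in SDs of the within-person difference. With one summary per immersion, omitting period multiplies the SE by sqrt(1 + r²): 1.03, 1.12 and 1.41 for r = 0.25, 0.5 and 1.0, which takes a nominal 80% power to 78%, 71% and 51%. The simulated false-positive rate for that analysis at n = 89 is 4.8–5.2% with or without period. With m scores per immersion, a random intercept only and equal sequences, the model SE is inflated by sqrt(1 + r²/(2m-1)): at r = 0.5 by 4%, 2% and 1% for m = 2, 4 and 8 (240/30 = 8 at most).

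**The case against.** The strongest reply is that order is randomised 1:1, so any imbalance is chance and period adjustment is mainly a matter of precision. That stands. A reader might infer that the missing term biases the primary result or inflates its error rate. The documents do not support that: attenuation is slight at modest period effects, the Cox false-positive rate does not move, and the power differences are of the order of the simulation error.

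A reader might also infer that all three models omit period. For the Cox and pain models this cannot be established, because the hand variables may already carry it. One route is easy to miss: if hand is coded per immersion and switches, a single interaction of hand used with dominant-hand-first is enough. The SAP states no interaction, but it does not exclude one.

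A third tempting inference is that a period term would restore the false-positive rate of the linear models with repeated scores. With a random intercept alone, no immersion-level variance and r = 0.5, simulation does give about 6–8% without the term and about 5% with it. But the SAP leaves the random-effects structure open. With immersion-level variance at 10% of the within-person variance, the rate is about 8–17% without the term and still 7–14% with it, while a test at immersion level without the term stays near 5%. That is mainly a question of random effects, and the period term should not be credited with solving it.

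**Conclusion.** The point holds as a minor one. The omission is clear for SCRD. For tolerance and pain it depends on coding that the SAP does not give: uncovered under plain main effects, covered under the three specific readings shown above. The cost is some lost precision, slight attenuation of the HR, and a VR estimate that moves with the realised split, by up to 0.06 on the HR scale at an assumed period HR of 1.5 and a 60/40 split. Only a large period effect (r near 1 in the linear models) would make the loss of power substantial, and nothing in the documents shows whether one exists. The conclusion rests on assumed period effects, on 89 as the number of pairs where that figure is used, and on a hand switch at the second immersion.

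**What to change.** First state how the two hand variables are coded and whether any interaction is fitted. Then add immersion number (1 versus 2) as a fixed effect to the SCRD model, and to the Cox and pain models unless the stated coding already contains it. Report the number of participants in each sequence. State that a period term does not remove differential carryover.

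The cost is one parameter per model. Immersion order is already known from the randomisation, and with no period effect the simulated power was about 80% with or without the term. The SAP is written in the past tense, so if the analysis has been done, present the adjusted result as a labelled sensitivity analysis beside the original estimate and do not replace it.

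### The pain-score and SCRD models name subject as the only grouping level, so on the plain reading the VR main-effect standard error is too small whenever readings within an immersion are correlated

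*SAP*

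**What the plan says.** In the SAP, under Measures, perceived pain "was assessed by collecting pain scores from participants every 30 seconds while their hands were immersed". SCRD is analysed over the same spacing: "We refer to each of these 30 second intervals as a separate epoch". Under Randomization, the first condition and the hand were allocated "using an electronic random number generator with a 1:1 allocation", and "Participants then crossed over for their second ice immersion". The protocol (section 2a, Procedures, Part 1b) has participants "keep hand submerged as long as they can withstand the cold or until 4 minutes" have passed.

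Under Statistical Methods, the primary outcome uses a "Cox mixed-effect model with trials nested in subject". For both secondary outcomes the description of the grouping is: "we used linear mixed effects models with outcomes nested in subject using the lme4 package in R". The pain model is adjusted for two dominant-hand variables (assignment and order) and gender. The SCRD model lists time and VR group.

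For the secondary models the SAP gives no formula, immersion level, by-subject VR effect, residual correlation structure or averaging to one value per immersion. The protocol does not describe these models.

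**The concern.** VR is constant throughout an immersion. Information on its effect comes from comparing a person's two immersions, and further readings in the same immersion add little if those readings move together. A subject random intercept treats two readings from the same immersion as no more alike than two readings from different immersions. Anything specific to one immersion, such as hand, order or that person's own response to VR, then counts as reading-level noise and is divided by the number of readings.

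The Cox model has one time per immersion, so clustering on subject is sufficient there. The secondary outcomes have several records per immersion, which is where an immersion level is needed, and none is named.

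At stake are the intervals and tests for VR's effect on pain intensity and on sympathetic response. Where the problem is present, it favours declaring an effect, and enrolling more people does not remove it.

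**Working it through.** **The plan's own figure.** The SAP gives no precision or power figure for the secondary models. Its one calculation (30 and 59 people, hazard ratio 0.6) concerns the primary outcome and does not enter here.

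**Inputs from the documents**
- Two immersions per person, one per condition (SAP, Randomization).
- One reading every 30 seconds (SAP, Measures) with a 4-minute cap (protocol, section 2a), so k is at most 240/30 = 8 readings per immersion.
- Subject as the only grouping level named (SAP, Statistical Methods).

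**Assumed.** rho is the share of within-subject variance lying between a person's two immersions. It is not in the documents and is varied from 0 to 0.5. The closed form takes k as equal in all immersions.

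**Formula.** Set the within-subject variance to 1, with rho between immersions and 1 − rho between readings.
- True variance of the VR effect, n people: (2/n)[rho + (1 − rho)/k] = (2/nk)[1 + (k − 1)rho].
- The subject-only model estimates its residual variance from 2k − 1 within-person degrees of freedom. Of these, 2(k − 1) have expectation 1 − rho and one has expectation 1 − rho + k·rho. The average is 1 − rho(k − 1)/(2k − 1), so the reported variance is (2/nk)[1 − rho(k − 1)/(2k − 1)].
- True/reported variance: R = [1 + (k − 1)rho] / [1 − rho(k − 1)/(2k − 1)].
- Actual two-sided type I error: 2[1 − Φ(1.96/√R)].

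**Worked case, k = 8, rho = 0.2.** The numerator is 1 + 7 × 0.2 = 2.4 and the denominator is 1 − 0.2 × 7/15 = 0.907. So R = 2.647 and √R = 1.627. The true standard error is 1.63 times the reported one. Then 1.96/1.627 = 1.205, which gives a type I error of 0.228.

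**Type I error at nominal 0.05**

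| Readings per immersion | rho 0 | 0.1 | 0.2 | 0.3 | 0.5 |
|---|---|---|---|---|---|
| 1 | 0.050 | 0.050 | 0.050 | 0.050 | 0.050 |
| 2 | 0.050 | 0.066 | 0.084 | 0.103 | 0.144 |
| 4 | 0.050 | 0.093 | 0.138 | 0.184 | 0.272 |
| 8 | 0.050 | 0.142 | 0.228 | 0.302 | 0.419 |

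n cancels from R, so a larger trial has the same inflation.

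**Simulation checks**
- Balanced, 2,000 runs per setting, k = 8. With 89 people the subject-only rate was 0.147 at rho 0.1 and 0.295 at rho 0.3; with 250 people it was 0.139 and 0.294. A paired analysis of immersion means held between about 0.04 and 0.06 in every setting run.
- Unequal durations (1 to 8 readings, 60 people, time term included, 120 to 150 runs per setting). The subject-only rates were 0.03, 0.08, 0.13, 0.19 and 0.23 at rho 0, 0.05, 0.1, 0.2 and 0.3. With an immersion intercept added they were 0.02 to 0.07. Simulation error for the inflated rates is about 2 to 4 percentage points.

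**Time-by-VR contrast.** With balanced data and no immersion-specific time slopes, a difference in slopes has true variance proportional to 1 − rho, while the subject-only model uses 1 − rho(k − 1)/(2k − 1). At k = 8 and rho = 0.2 these are 0.80 and 0.907, so the reported standard error is slightly too large. The understatement therefore concerns the VR main effect.

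**The case against.** The faulty model is inferred from one phrase. A by-subject VR effect also has subject as its only grouping factor and would handle the problem. One mean score per immersion would also do so, and the pain model lists no time term, so reading-level rows are less certain for pain than for SCRD. This stands as a limit on certainty. The SAP states neither alternative, however, and an analyst who follows the text as written would most naturally fit a subject intercept to the readings.

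The SCRD wording does not settle whether VR is tested as a difference in level or in change over time, and in the second case the direction need not hold. That also stands.

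Some sources of between-immersion variance may be small. The protocol (section 2b) has the bath temperature constantly monitored, and active participation lasts about one hour (section 5m). The pain model does adjust for hand. As named, though, the hand variables take one value per person, and as main effects such terms cannot absorb a difference between that person's two immersions. If they were coded per immersion, they would remove the average hand or order difference but not a person's own response to VR.

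A reader might infer that both secondary intervals are certainly too narrow and that their false-positive rate is well above 5%. The documents do not support that: they give neither rho nor the number of readings per immersion, and 8 readings is only the ceiling.

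**Conclusion.** The point holds in conditional form. With one row per reading and a subject random intercept, any positive rho with more than one reading per immersion makes the VR main-effect standard error too small. The type I error ranges from 5% (rho of 0, or a single reading) to about 42% (rho 0.5, 8 readings). At rho 0.1 to 0.2 with 4 to 8 readings it is about 9% to 23%. These figures rest on assumed rho, equal k and the plain reading of the SAP. They do not carry over to a time-by-VR contrast, nor to the primary analysis, which has one record per immersion.

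This is more than missing detail, because the structure as worded gives wrong error bars if followed. Only secondary outcomes are affected and the size is unknown, so it is a should-fix.

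**What to change.** In the SAP's Statistical Methods, for both secondary models, replace the subject-only grouping with readings nested in immersion and immersions nested in subject: `(1 | subject/immersion)`, or an equivalent by-subject random VR effect. Print the full formula. Base the degrees of freedom for VR on the number of people, not the number of readings.

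State whether the SCRD contrast is a difference in level or in change over time. If it is the latter, also add a random time slope by immersion. An immersion intercept does not itself model serial correlation between neighbouring readings.

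Re-report both VR estimates and intervals. If an adequate structure was already fitted, printing its formula resolves the point.

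The cost is a small change to the random-effects terms and a re-run on existing data. The secondary intervals may widen; if rho is near zero they will barely change.
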